5.1.4.2 Dose Escalation Scheme

The avelumab dose escalation will be performed in cohorts of 3 subjects each according to the following dose levels with a 3 or 3.3 times of dose increase at each escalation:

- 1.0 mg/kg
- 3.0 mg/kg
- 10.0 mg/kg

[figure not shown]
The dose escalation criteria are as follows:

For each dose level, DLTs are assessed during the first 3 weeks. The criteria for moving from one dose level to another do not allow escalation to the next cohort in cases where ≥ 2 of 3 or 6 subjects in a cohort experience a DLT. If 1 of 3 subjects in a cohort experiences a DLT, this cohort will be expanded to 6 subjects. The MTD is defined as the highest dose where fewer than 2 of 6 subjects experience a DLT. Thus, the MTD cohort should accrue at a total of 6 subjects.

Once the MTD or maximum dose to be investigated is reached, the respective dose level cohort will be filled to a total of 6 subjects. Once the dose of 10 mg/kg is established as safe, 10 additional subjects at 3 mg/kg and 10 mg/kg each may be enrolled, for the purpose of generating additional safety, PK and receptor occupancy data, if agreed with the SMC.

A schematic of dose escalation is presented in [Figure 5.2](#).

Figure 5.2 Dose Escalation Algorithm for Doses up to 10 mg/kg

Abbreviations: IMP: investigational medicinal product; DLT: dose-limiting toxicity; MTD: maximum tolerated dose.

Each subject will stay on the dose level assigned at trial entry. The first subject of each cohort should be observed for 16 days (i.e., 48 hours after the second dose) for DLT occurrence before the second subject is to be administered the trial medication. Thereafter, within each cohort of the dose escalation phase, subjects may only be consecutively dosed with an interval of at least 48 hours. However, after 3 subjects have been treated at 10 mg/kg and no DLT has been observed, the other 3 subjects required to complete this cohort can be enrolled without sequential dosing (i.e., not required to wait until 48 hours). If no more than 1 DLT has been observed in these 6 subjects, the safety of 10 mg/kg will have been established.

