5.1.7.2 ADRs Requiring Treatment Discontinuation or Modifications

The following ADRs require permanent treatment discontinuation of avelumab:

Any Grade 4 ADRs require treatment discontinuation except for single laboratory values out of normal range that are unlikely related to trial treatment as assessed by the investigator, do not have any clinical correlate, and resolve within 7 days with adequate medical management.

Any Grade 3 ADRs require treatment discontinuation except for any of the following:

- Transient (≤ 6 hours) Grade 3 flu-like symptoms or fever, which is controlled with medical management.
- Transient (≤ 24 hours) Grade 3 fatigue, local reactions, headache, nausea, emesis that resolves to \leq Grade 1.
- Single laboratory values out of normal range (excluding \geq Grade 3 liver function test increase) that are unlikely related to trial treatment according to the investigator, do not have any clinical correlate, and resolve to \leq Grade 1 within 7 days with adequate medical management.
- Tumor flare phenomenon defined as local pain, irritation, or rash localized at sites of known or suspected tumor.
- Any Grade ≥ 3 drug-related amylase or lipase abnormality that is not associated with symptoms or clinical manifestations of pancreatitis does not require dose delay. The Study Medical Monitor should be consulted for such Grade ≥ 3 amylase or lipase abnormalities.
- Increases in ECOG performance status ≥ 3 , which do not resolve to ≤ 2 by cycle Day 14 of the following cycle (infusions should not be given on the following cycle, if the ECOG performance status is ≥ 3 on the day of study drug administration).

Any Grade 2 ADR should be managed as follows:

- Infusion should not be given in case of ongoing Grade 2 ADR on the day of trial treatment administration.
- Treatment can be resumed according to original schedule once ADR resolved to Grade ≤ 1 . Up to 2 subsequent study drug doses may be omitted. If more than two doses are skipped, treatment may be resumed after consultation with study Medical Monitor.
- Infusion-related reactions, hypersensitivity reactions (Grades 1 to 4), tumor lysis syndrome, and irAEs should be handled according to the guidelines provided in Sections [6.5.4.1](#), [6.5.4.2](#), [6.5.4.3](#), [6.5.4.4](#), respectively.

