5.5 Criteria for Subject Withdrawal

5.5.1 Withdrawal From the Trial

Subjects are free to discontinue the trial at any time without giving their reasons.

A subject must be withdrawn in the event of any of the following:

- Withdrawal of the subject's consent.
- Participation in any other therapeutic trial during the treatment duration of this trial.

If a subject has failed to attend scheduled trial assessments, the investigator must determine the reasons and the circumstances as completely and accurately as possible.

In case of premature withdrawal from the trial, the investigations scheduled for the last visit should be performed (see Section 7.1.3 for end-of-treatment visit), if possible, with focus on the most relevant assessments. In any case, the appropriate case report form (CRF) section must be completed.

In the dose escalation part of the trial, only subjects who do not complete the DLT observation period (3 weeks) for reasons other than a DLT will be replaced. Subjects who require discontinuation of avelumab due to a DLT will not be replaced. In the expansion part of the trial, if a subject is withdrawn prior to progression for any reason, they will not be replaced except for the rule described above.

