8.4 Analysis Sets

The following analysis sets will be defined separately for the dose escalation part and the expansion cohorts in this trial, as applicable:

- **DLT population (dose escalation part):** all subjects with data used for implementing the dose-escalation schedule. These subjects should have received all study treatment administrations in the DLT evaluation period or should have stopped treatment because of DLTs in the DLT evaluation period.
- **Safety population:** all subjects who have received at least 1 dose of trial treatment.
- **Full analysis set (FAS):** all subjects who have received at least 1 dose of trial treatment.
- **PD-L1 positive FAS (urothelial carcinoma efficacy expansion cohort):** all PD-L1+ subjects who have received at least 1 dose of trial treatment.
- **PK population:** All subjects who have completed at least 1 infusion of study drug, and who have provided sufficient concentration measurements.
- **Efficacy population (efficacy expansion cohorts):** all subjects who have received at least 1 dose of trial treatment and have measurable disease at baseline according to IERC assessment.
- **PD-L1 positive efficacy population (urothelial carcinoma efficacy expansion cohort):** all PD-L1+ subjects who have received at least 1 dose of trial treatment and have measurable disease at baseline according to IERC assessment.

- **Efficacy population (primary and secondary expansion cohorts):** all subjects who have received at least 1 dose of trial treatment and have measurable disease at baseline according to investigator assessment.

The definition of the Safety Population and the FAS are identical in this non-randomized study; the Safety population will be used for the safety analysis and the FAS will be used for efficacy analysis. The PD-L1 positive FAS will be the primary analysis population for the primary endpoint of BOR by IERC in the urothelial carcinoma efficacy expansion cohort.

PD-L1 status is assessed by immunohistochemistry. Subjects will be considered PD-L1 positive (negative) for the urothelial carcinoma efficacy expansion cohort if at least (less than) 5% of the tumor cells show PD-L1 membrane staining, respectively. If during assay development (based on generic samples) a different cut-off is determined to be more appropriate, this cut-off may be adapted in the SAP prior to analysis of subject samples from this trial.

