8.5.2 Analysis of Primary Endpoints

8.5.2.1 Maximum Tolerated Dose Determination

For determination of the MTD, individual subject data from the dose escalation part will be reported.

In addition, for the final statistical analysis, the following will be analyzed:

- At each dose level, the number and proportion of subjects in the DLT population who experience a DLT during the first DLT evaluation period.
- At each dose level, the number and proportion of TEAEs experienced by subjects in the DLT population during the first DLT evaluation period.

The MTD will be determined according to the dose-escalation plan described in Section 5.1.4.2. The MTD is defined as the highest dose level at which no more than 1 subject out of 6 subjects treated in a cohort and evaluable for DLT determination experiences a DLT.

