	
48 hours between 2 subjects). This additional cohort will have the purpose of generating safety data, PK data and receptor occupancy data at the respective dose.
 
Definition of DLT
 
A DLT is specifically defined as any Grade ≥ 3 toxicity that is possibly, probably, or definitely related to avelumab, occurring during the DLT evaluation period (21 days after administration of avelumab), except for any of the following:
 
 • Grade 3 infusion-related reaction resolving within 6 hours and controlled with medical management. • Transient (≤ 6 hours) Grade 3 flu-like symptoms or fever, which is controlled with medical management. • Transient (≤ 24 hours) Grade 3 fatigue, local reactions, headache, nausea, emesis that resolves to \leq Grade 1. • Grade 3 diarrhea, Grade 3 skin toxicity, or Grade 3 liver function test (ALT, AST, or GGT) increase that resolves to \leq Grade 1 in less than 7 days after medical management (e.g., immunosuppressant treatment) has been initiated. • Single laboratory values out of normal range that are unlikely related to trial treatment according to the investigator, do not have any clinical correlate, and resolve to \leq Grade 1 within 7 days with adequate medical management. • Tumor flare phenomenon defined as local pain, irritation, or rash localized at sites of known or suspected tumor. 
DLTs requiring treatment discontinuation are described in Section 5.1.7.2 of Protocol Amendment 12.
 
Subjects who do not complete the DLT observation period for reasons other than a DLT will be replaced.
 
Expansion phase
 
This section was included into the Expansion SAP.

Number of Subjects
	
Dose escalation phase: 18 up to 60 subjects.
 
The final sample size, however, will depend on the total number of dose levels to be tested, and subject replacement for DLT evaluation if applicable.

Trial Product
	
Avelumab will be administered as a 1-hour (-10 minutes /+20 minutes, i.e., 50-80 minutes) i.v. infusion. Subjects will receive avelumab once every 2

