	
All subjects will have a subsequent visit scheduled 10 weeks after the last administration of avelumab. The visit will include a full assessment of safety parameters.
 
AEs will be documented until the end of treatment visit. After the end of treatment visit only treatment related AEs have to be documented until the post-treatment safety follow-up visit. Subjects with a serious AE ongoing at the post-treatment safety follow-up must be monitored and followed up by the investigator until stabilization or until the outcome is known, unless the subject is documented as “lost to follow-up”.
 
Subjects without progressive disease at the end-of-treatment visit will be followed up for disease progression (CT / MRI scans every 12 weeks) up to 1 year. In addition, subjects will be followed for any AE suspected to be related to trial treatment, especially for the occurrence of new autoimmune events up to 3 months after the last dose of avelumab.
 
After the end-of-treatment visit, subjects will be followed quarterly for survival (including assessment of any further tumor therapy). The survival follow-up will continue until 1 year after the last subject receives the last dose of avelumab.
 
For dose expansion cohorts
 
This section was included into the Expansion SAP.

Randomization and Blinding	Not applicable.

8 Overview of Planned Analyses

There will be one planned analysis after the end of dose escalation phase. This SAP will only address the analysis for the dose escalation phase. Additional SAPs for SMC analyses and for all other analyses (interim, primary, and final) for expansion cohorts have been developed separately.

9 Changes to the Planned Analyses in the Clinical Trial Protocol

The data cut-off date was changed to Nov 20, 2015 from 6 weeks after the last subject of the dose escalation part has received its first administration of avelumab in order to provide a more comprehensive evaluation of the dose escalation phase in the first interim CTR for this study.

10 Analysis Sets

The following analysis sets will be defined for the dose escalation part:

- Screening analysis set: all subjects who signed the informed consent form (ICF).
- DLT analysis set: all subjects with data used for implementing the dose-escalation schedule. These subjects should:
 - Have received all study treatment administrations during the DLT evaluation period (first 21 days of treatment) or

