16.1 Primary Endpoint Analysis

The primary endpoint in the dose escalation part of this trial is the occurrence of DLTs during the DLT evaluation period.

A DLT is defined as a Grade ≥ 3 adverse drug reaction according to the NCI-CTCAE v4.0, occurring during the DLT evaluation period confirmed by the SMC to be relevant for the study drug treatment based on the criteria specified in Protocol.

The summary of DLTs will include the following variables by dose level and overall for the DLT analysis set:

-
- the number and percentage of subjects who experienced a DLT during the DLT evaluation period
 - number of DLT per subject, 1 /2 /≥3
 - DLT by SOC and PT

The number and percentage of subjects who experienced a TEAE by SOC and PT during the DLT evaluation period will also be summarized by dose level and overall for the DLT analysis set. A listing of DLT AEs will include dose level, subject identifier, SOC/PT, and all relevant variables, such as start/stop date, toxicity grade, relationship to the study treatment, outcome etc., from AE eCRF page.

The MTD or maximum dose will be determined according to the dose-escalation plan described in section 5.1.4.2 of trial protocol. The MTD or maximum dose is defined as the highest dose level at which no more than one out of 6 subjects treated in a cohort and evaluable for DLT determination experiences a DLT.

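### Replacement turns on completing 21 days and DLT-set membership on doses received, so a DLT-free subject with a held Day 15 dose leaves the denominator and cannot be replaced

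*Protocol*

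**What the plan says.** - **Replacement.** Protocol 5.5.1, for the escalation part: "only subjects who do not complete the DLT observation period (3 weeks) for reasons other than a DLT will be replaced". Protocol 5.1.4.3 has the same trigger without the word only, as does dose-escalation SAP 6: "Subjects who do not complete the DLT observation period for reasons other than a DLT will be replaced".
- **DLT set.** Protocol 8.4: "These subjects should have received all study treatment administrations in the DLT evaluation period or should have stopped treatment because of DLTs", both within the evaluation period. Dose-escalation SAP 10 gives the same two limbs, the first being "Have received all study treatment administrations during the DLT evaluation period (first 21 days of treatment) or" and the second a stop because of a DLT.
- **MTD.** The condition that a dose must meet in Protocol 8.5.2.1 is this: "no more than 1 subject out of 6 subjects treated in a cohort and evaluable for DLT determination experiences a DLT". SAP 16.1 says "no more than one out of 6 subjects treated in a cohort and evaluable for DLT determination experiences a DLT". Protocol 8.5.1 makes the DLT population the basis for determining the MTD.
- **Held doses.** Protocol 5.1.7.2: "Infusion should not be given in case of ongoing Grade 2 ADR on the day of trial treatment administration". Treatment then resumes on the original schedule, and up to two doses may be left out.
- **Decision point.** Under Protocol 5.1.4.2 the safety monitoring committee reviews a cohort once all its subjects have completed Day 21. Nothing there asks how many doses each subject received.

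**The concern.** The two rules sort the same subjects by different tests. One asks whether the subject was observed for three weeks, the other whether the subject was dosed in full. A held Day 15 dose separates them without anything unusual happening: the subject stays on study, reaches Day 21, fails the dosing test, and does not qualify for replacement.

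Inclusion then depends on the outcome. Among subjects with a held dose, those who have a DLT enter the primary analysis set and those who do not are dropped. This affects the primary endpoint of the escalation phase, both the count of evaluable subjects that the MTD definition requires and the DLT percentage tabulated by dose level.

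**Working it through.** **1. Doses in the window.** Dosing is every 14 days from Day 1, so Days 1 and 15 fall within the first 21 days and the next scheduled dose is Day 29. This agrees with Protocol 5.1.4.2, where the first subject of each cohort is "observed for 16 days (i.e., 48 hours after the second dose": 14 + 2 = 16. The general visit window is -3/+1 days (Protocol 7.1.2), so a reaction that resolves by Day 16 need not cost the dose. One that lasts longer moves dosing to Day 29, outside the window.

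**2. How each kind of subject is classified.**

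| Subject | In DLT set? | Replaceable under 5.5.1? |
|---|---|---|
| Both doses, Day 21 reached, no DLT | Yes | No |
| Day 15 held, Day 21 reached, no DLT | No | No |
| Day 15 held, DLT by Day 21 | Yes, since the Synopsis ends treatment on any DLT | No |
| Leaves before Day 15, no DLT | No | Yes |

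The second row is the gap. Subjects added later at a dose level cannot fill it, because Protocol 5.1.4.3 gives them no DLT observation period.

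**3. Effect on the MTD definition.** One such subject in a filled cohort of 6 leaves 5 evaluable. The definition needs 6, and no passage says what follows when there are fewer.

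**4. Effect on the reported proportion.** Let p be the true DLT rate and h the fraction of subjects with a held Day 15 dose, independent of DLT. The set keeps all subjects with a DLT (p) and the DLT-free subjects who were not held, (1 - p)(1 - h). The expected reported proportion is

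p / [p + (1 - p)(1 - h)] = p / [(1 - h) + hp].

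The documents give neither p nor h, so both are assumed. With p = 0.20:

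- h = 0.10: 0.20 / 0.92 = 21.7%
- h = 0.20: 0.20 / 0.84 = 23.8%
- h = 0.30: 0.20 / 0.76 = 26.3%

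Only holds among DLT-free subjects remove anyone, so the bias is upward even if holds and DLTs are related. In a single cohort, 1 DLT in 6 (16.7%) becomes 1 in 5 (20.0%) when one DLT-free subject is dropped.

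**5. How often a cohort of 6 would be touched.** The chance that a given subject is dropped is h(1 - p). With p = 0.20, the chance that at least one of 6 is dropped is:

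- h = 0.10: 1 - 0.92^6 = 39.4%
- h = 0.20: 1 - 0.84^6 = 64.9%
- h = 0.30: 1 - 0.76^6 = 80.7%

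There is no power or error rate in the plan to reproduce here. Protocol 8.1 says that the escalation sample size rests on no statistical assumptions.

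**The case against.** The strongest case on the other side has four parts.

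- **The text is looser than this reading.** The DLT population opens with subjects whose data were used to implement the escalation, and the dosing condition is worded with should. The Synopsis and Protocol 5.1.5 mention replacement for DLT evaluation where applicable. This makes the position ambiguous, but it does not close the gap: 5.5.1 restricts replacement with the word only, the remaining sentence in 5.1.5 concerns drop-outs, and no passage says that a held subject counts as evaluable.
- **The committee sees everyone.** Its review is not limited to the DLT set, and adverse events of all treated subjects are summarised on the safety set. This stands: the toxicity of a held subject is not hidden from the decision. The analysis denominator can still differ from the one the committee had in view.
- **The bias is conservative.** This also stands. Dropping DLT-free subjects overstates toxicity. It is still an error in a primary result, and its size will vary by dose level with the number of holds.
- **The cohorts are closed.** Protocol 3.5.1 reports the escalation safety analysis as complete and the MTD as not reached. The once-weekly cohort has no DLT endpoint and its own replacement rule (Protocol 5.1.1). Replacement can no longer be applied to the every-2-week cohorts, so only the reporting part can still be acted on there.

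**Conclusion.** The point holds as an inconsistency with two consequences: an evaluability count that the replacement rule cannot guarantee, and an upward bias in the DLT proportion. On average a true 20% is reported as 21.7 to 26.3% at an assumed 10 to 30% of subjects held. The documents do not say whether any Day 15 dose was held, so the actual effect may be nil.

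Two stronger conclusions might be inferred, and the documents do not support either.

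- A reader might say that the MTD can be declared on fewer than 6 subjects. No passage permits at most 1 DLT in 5. With 5 evaluable the definition is unmet, and the plan does not say what happens next.
- A reader might say that the rule becomes easier to pass, by putting 5 in place of 6 in the binomial. At an assumed DLT rate of 33% that would raise the chance of at most 1 DLT from 35.8% to 46.8%. This treats subjects as lost whatever their outcome. Here a held subject who has a DLT stays in the set, so DLTs are still counted over all 6 treated and the figure remains 35.8%.

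A held subject also has one dose in the window instead of two, so 21 DLT-free days tell less about that dose level. The documents give nothing from which to size this.

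**What to change.** Reconcile Protocol 5.1.4.3, 5.5.1 and 8.4 with dose-escalation SAP 6 and 10 on a single evaluability criterion. Either of two would do:

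- every subject who fails the DLT-set definition is replaceable; or
- every subject observed for 21 days, or with a DLT, is evaluable.

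The first may need a few extra subjects. The second needs none but counts some subjects with reduced exposure. The text should also say what follows when fewer than 6 are evaluable.

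For the completed every-2-week cohorts, add to the DLT summary in dose-escalation SAP 16.1 the DLT incidence by dose level among all subjects who completed 21 days or had a DLT, beside the DLT-set result. Give the number non-evaluable at each dose level with the reasons. This costs one table row and a short listing. No change to any dosing or treatment-holding rule is proposed.

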5.5.2 Withdrawal From the Investigational Medicinal Product

The subject must be withdrawn in the event of any of the following:

- Occurrence of an exclusion criterion, which is clinically relevant and affects the subject's safety, if discontinuation is considered necessary by the investigator and/or Sponsor.
- Therapeutic failure requiring urgent additional drug (if applicable).
- Occurrence of any Grade ≥ 3 ADRs as defined in Section 5.1.7.
- Occurrence of AEs, resulting in the discontinuation of trial drug being desired or considered necessary by the investigator and/or the subject (if applicable).
- Occurrence of pregnancy (if applicable).
- Use of a non-permitted concomitant drug, as defined in Section 6.5.2, where the predefined consequence is withdrawal from the IMP (the Sponsor may be contacted to discuss whether the trial treatment must be discontinued).
- Non-compliance (see Section 6.9).

